1.0 Background

Each year, thousands of hysterectomies are performed for various indications including cancer, fibroids, endometriosis, and other conditions. Laparoscopic hysterectomy is often complicated by post-operative pain, making pain control challenging especially with the use of opioids. Improved pain control increases patient satisfaction and may lead to improved postoperative course.[1, 2] Our standard of practice at Indiana University Hospital is to perform Transverse Abdominis Plane (TAP) block using liposomal bupivacaine (LB) for these patients to help with postoperative analgesia. [3] Recent literature suggests that Erector Spinae Plane (ESP) block may be a safe and effective alternative for thoracic, extremity, and abdominal surgeries. [4] Currently there are numerous case reports supporting use of ESP block [5] but there are not prospective randomized controlled trials comparing these 2 blocks to date. . Our study aims to compare the efficacy of ESP block and TAP block in laparoscopic hysterectomy.

The ESP block, first described by Forero in 2016, provides regional anesthesia targeting in the range of the T2-L1 branches of thoracolumbar nerves.[6] The ultrasound is positioned in a parasagittal fashion, lateral to the spinous process, to visualize the transverse process. The needle is inserted cranial-to-caudal in plane traversing through the trapezius muscle, the rhomboid major muscle, and the erector spinae muscles, aiming to make contact with the transverse process, with the needle tip deep to the plane of the erector spinae muscle, which overlies the transverse process. Injection of saline confirms the correct location of the needle as determined by cranio-caudal spread of saline under the erector spinae muscle, “lifting” it off of the transverse process. Once the correct location is identified, the local anesthetic is injected.

We plan to use Exparel®, or a liposomal formulation of bupivacaine, as the analgesia for both arms of the study. Because Exparel® is in liposomal form, the lipid solubility allows bupivacaine to be released over an extended period of time. It is reported to provide long-lasting analgesia for up to 72 hours and may result in decreased opioid consumption and shortened hospital stays. [7] There is no current standard of practice for local anesthesia in ESP block. LB has good analgesia coverage for up to 72 hours postoperative when compared to normal saline and has been suggested to reduce postoperative opioid use as well. [8, 9]

2.0 Rational and Specific Aims

Both of the pain control modalities in this study have been used as postoperative analgesia in prior studies. The specific aim of this study is to compare the difference between the pain control methods in achieving the following:

1. Decreased opioid requirements
2. Improved postoperative pain scores
3. Decreased opioid side effects (Nausea, sedation, ileus, urinary retention, respiratory depression)

The primary endpoint of this study will be VAS pain score. The VAS scores will be taken with both rest and movement.

The secondary endpoint includes intravenous opioid consumption and opioid side effects (nausea, sedation, ileus, urinary retention, respiratory depression). The IV and PO opioid doses will be quantified at 1, 24, and 48 hours. We will also measure postoperative nausea and sedation scores at 1, 24 and 48 hours. We will also assess patient satisfaction postoperative at 24 and 48 hours. We will also measure time to first flatus, incidence of urinary retention, incidence of respiratory depression, ambulation activity, and hospital length of stay.

3.0 Inclusion/Exclusion

Inclusion criteria:

- Patients undergoing laparoscopic hysterectomy surgery at Indiana University Hospital
- ASA class 1, 2, 3 or 4
- Age 18 or older, female
- Desires Regional anesthesia for postoperative pain control

Exclusion criteria:

- Any contraindication for ESP or TAP block.
- History of substance abuse in the past 6 months.
- Patients on more than 30 mg morphine equivalents of opioids.
- Any physical, mental or medical conditions which in the opinion of the investigators, may confound quantifying postoperative pain resulting from surgery.
- Known allergy or other contraindications to the study medications (Acetaminophen, Gabapentin, Bupivacaine).
- Postoperative intubation.
- Any BMI greater than 40.0.

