4.0 Enrollment/Randomization

All laparoscopic hysterectomy cases scheduled by OBGYN at IU Health University Hospital will be identified. Subjects will be contacted face-to-face prior to surgery. They will be informed about the study and all questions will be answered. All patients will undergo a standardized enhanced recovery perioperative care pathway designed and agreed upon by the perioperative team of anesthesiologists and surgeons.

A total of 80 subjects will be randomized by a computer program into two groups (40 in each group):

1. TAP block – placed by ultrasound using 266mg Exparel (20ml) and 60ml of 0.125% bupivacaine. 40ml on each side. 20ml injected for subcostal TAP and 20ml injected for posterior TAP.

2. ESP block – placed by ultrasound using 266mg Exparel (20ml) and 60ml of 0.125% bupivacaine. 40ml on each side. 20ml injected at T8 and 20ml injected at T12

Randomization will be performed using a block randomization of the 2 groups instead of a simple 2-group randomization to keep the study groups fairly balanced throughout enrollment. The primary investigator will inform the person doing the block as to what group the patients are randomized to. Both the patients and the research staff doing assessments will be blinded to the randomization.

5.0 Study procedures:

The TAP blocks will be placed intraoperatively after induction, while ESP blocks will be done preoperatively. All procedures will be done using sterile technique with masks, hats, and sterile gloves. All procedures will be placed under the supervision of the attending anesthesiologist on the acute pain service.

For the TAP block, the ultrasound probe is placed transverse to the abdominal wall, between the iliac crest and the costal margin. The needle is placed in the plane of the probe and advanced until it is between the internal oblique and the transversus abdominis muscles. Once in the plane, 2 mL of saline is injected to confirm needle position, then the local anesthetic solution is injected. [10]

For the ESP block, as mentioned previously, the ultrasound is positioned in a parasagittal fashion, 2-3 inches lateral to the spinous process. This approach visualizes the transverse process. The needle is inserted cranial-to-caudal to make contact with the shadow of the transverse process, with the needle tip deep to the fascial plane of the erector spinae muscle. Injection of saline confirms the location of the needle, and the anesthetic is injected.

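### Every assignment in a blocked sequence passes through the primary investigator, eligibility has an untimed opinion-based exclusion, and no allocation concealment is described, so selection into the arms is possible, though not shown

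*Combined protocol and SAP*

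**What the plan says.** Section 4.0 has a computer program randomize 80 subjects, 40 per group. On method it says: "Randomization will be performed using a block randomization of the 2 groups instead of a simple 2-group randomization". It gives no block size and does not say whether the size varies. The only route described for an assignment is: "The primary investigator will inform the person doing the block as to what group the patients are randomized to". Blinding is defined as: "Both the patients and the research staff doing assessments will be blinded to the randomization". Neither the primary investigator nor whoever decides eligibility is covered by that sentence.

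On recruitment, Section 4.0 says only "Subjects will be contacted face-to-face prior to surgery". It does not name who approaches the patient or who confirms eligibility.

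Section 3.0 includes a discretionary exclusion: "Any physical, mental or medical conditions which in the opinion of the investigators, may confound quantifying postoperative pain resulting from surgery". It has no objective test, no time by which it must be decided, and no requirement to record a reason. The same list contains "Postoperative intubation", which can be known only after surgery.

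**The concern.** Three features combine. One person learns every assignment as the trial accrues. Blocking makes past assignments informative about the next one. The eligibility rules leave room for judgement on the very thing the primary endpoint measures, postoperative pain. The primary investigator would ordinarily count among the investigators whose opinion applies.

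If someone judging eligibility can foresee the next arm, candidates expected to have more pain could be refused, knowingly or not, when one arm is next and accepted when the other is next. The primary hypothesis in Section 8.0 favours ESP, which gives such a tendency a direction. Enrolment runs until 80 subjects are reached (Section 10.0), so a refused candidate is simply replaced.

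Blinded VAS scoring does not protect against this, because the groups would already differ before anyone is scored. Nor does the planned repeated measures model, whose fixed effects are group, time and their interaction.

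**Working it through.** **1. The plan's own figure.** Inputs from Section 8.0: coefficient of variation 0.70, 40 per group, ratio of means 1.6, two-sided 5%, power 90%.
- Log-scale SD = √ln(1 + 0.70²) = √ln 1.49 = 0.631.
- SE of the difference = 0.631 × √(2/40) = 0.141.
- ln 1.6 = 0.470.
- Power is 0.914 (normal) or 0.908 (noncentral t, 78 df). The stated 90% reproduces. This point does not dispute the sample size; the same SD and SE are reused below.

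**2. Predictability of a blocked sequence.** Assumptions, since the plan is silent: 1:1 permuted blocks of fixed, known size, with all earlier assignments seen. Every possible block was enumerated. An assignment is certain once one arm is used up within the block. The best guess is the arm with more places left, and ties are a coin toss.

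| Block size | Next assignment certain | Out of 80 | Guessed correctly |
|---|---|---|---|
| 2 | 50% | 40 | 75% |
| 4 | 33% | about 27 | 71% |
| 6 | 25% | 20 | 68% |
| 8 | 20% | 16 | 67% |

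Under simple randomization no assignment is certain, and 50% are guessed correctly.

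**3. Illustrative upper bound on type I error.** Assumptions not in the documents: 30% of candidates are recognisably high-pain, their VAS is 1.6 times that of the rest, and every one of them is refused whenever ESP is expected. There is no true difference between the blocks. The log-scale bias is the difference in high-pain share between arms times ln 1.6.

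*Blocks of 4 (correct guess 0.708):*
- High-pain share in ESP = 0.30 × (1 − 0.708) = 8.75%; in TAP = 0.30 × 0.708 = 21.25%.
- Bias = 0.125 × 0.470 = 0.0588; z shift = 0.0588 / 0.141 = 0.42.
- Type I error = 1 − Φ(1.96 − 0.42) + Φ(−1.96 − 0.42) = 7.0%.

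*Whole list known:*
- High-pain share 0% in ESP, 30% in TAP.
- Bias = 0.30 × 0.470 = 0.141; z shift = 1.00.
- Type I error = 17.0%.

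A simulation of the same scenarios, with log-normal data, 40 per arm and t-tests, gave about 6.7% and 16%. It is slightly lower because mixing patient types adds variance.

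**The case against.** A reader might infer that allocation is not concealed and that entry to each arm can be steered. The documents do not support that. Section 4.0 has a computer program randomize and the primary investigator then pass the result on, which is compatible with release only after enrolment. No section says that the primary investigator holds the list, sees an assignment before eligibility is settled, or personally applies the opinion-based exclusion. This objection stands, and the point is limited to what is not described.

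The discretionary exclusion is also a common type of clause and would be harmless under concealed allocation. That stands too: the gap lies in Section 4.0, and the exclusion only contributes to it. A reader might add that ordinary indications named in Section 1.0, such as endometriosis or cancer, could be refused as confounders of pain. Nothing in the plan suggests this.

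The assumptions on size are extreme and have no source. The 1.6 is the plan's detectable ratio between arms, borrowed here as a difference between patient types. A larger error of about 22% for a known list comes from taking the log of the ratio of arithmetic means (1.18) and dividing by the log-scale SE. That mixes scales; the same assumptions give about 17%.

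The objection does not remove one thing. Even if each assignment is released only after enrolment, the person relaying it has seen all earlier ones, and in a blocked sequence later ones stay partly predictable. Because ESP blocks are placed preoperatively (Section 5.0), an ESP assignment must also be out before surgery, and nothing says eligibility is closed by then.

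**Conclusion.** The point holds as a gap in the described procedure, not as a demonstrated bias. The plan routes every assignment through someone who is naturally among those whose opinion can exclude patients, uses blocks, and describes no concealment or timing safeguard.

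The predictability figures, 20% to 50% of assignments certain and 67% to 75% guessed correctly, rest on a fixed, known block size from 2 to 8 and sight of past assignments. The type I errors of about 7% and 17% further assume complete refusal of an assumed high-pain group. They are ceilings under those assumptions, not forecasts. The documents give no basis for choosing a value within the range.

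A change should be made because this kind of bias cannot be repaired after enrolment and is cheap to prevent. If the safeguards already exist in practice, writing them down is enough.

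**What to change.** Amend Sections 3.0 and 4.0 as follows.

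1. All eligibility criteria that can be judged before assignment, including the opinion-based exclusion and its reason, are completed and locked in REDCap before the assignment is released. No patient is excluded under the opinion-based criterion after release.
2. REDCap releases the assignment directly to the person doing the block. The primary investigator and anyone else judging eligibility see neither current nor past assignments. The person doing the block therefore does not judge eligibility. State who generates and holds the sequence.
3. Block sizes vary at random and are not disclosed to those who enrol.

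A log of identified candidates who were refused, with reasons, is optional good practice.

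The cost is protocol wording and set-up in a system that Section 9.0 already names for data collection; whether it is set up for randomization is not stated. The primary investigator gives up the relay role, and one short form is locked per patient. The sample size and the analysis do not change.

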4.0 Enrollment/Randomization

All laparoscopic hysterectomy cases scheduled by OBGYN at IU Health University Hospital will be identified. Subjects will be contacted face-to-face prior to surgery. They will be informed about the study and all questions will be answered. All patients will undergo a standardized enhanced recovery perioperative care pathway designed and agreed upon by the perioperative team of anesthesiologists and surgeons.

A total of 80 subjects will be randomized by a computer program into two groups (40 in each group):

1. TAP block – placed by ultrasound using 266mg Exparel (20ml) and 60ml of 0.125% bupivacaine. 40ml on each side. 20ml injected for subcostal TAP and 20ml injected for posterior TAP.

2. ESP block – placed by ultrasound using 266mg Exparel (20ml) and 60ml of 0.125% bupivacaine. 40ml on each side. 20ml injected at T8 and 20ml injected at T12

Randomization will be performed using a block randomization of the 2 groups instead of a simple 2-group randomization to keep the study groups fairly balanced throughout enrollment. The primary investigator will inform the person doing the block as to what group the patients are randomized to. Both the patients and the research staff doing assessments will be blinded to the randomization.

5.0 Study procedures:

The TAP blocks will be placed intraoperatively after induction, while ESP blocks will be done preoperatively. All procedures will be done using sterile technique with masks, hats, and sterile gloves. All procedures will be placed under the supervision of the attending anesthesiologist on the acute pain service.

For the TAP block, the ultrasound probe is placed transverse to the abdominal wall, between the iliac crest and the costal margin. The needle is placed in the plane of the probe and advanced until it is between the internal oblique and the transversus abdominis muscles. Once in the plane, 2 mL of saline is injected to confirm needle position, then the local anesthetic solution is injected. [10]

For the ESP block, as mentioned previously, the ultrasound is positioned in a parasagittal fashion, 2-3 inches lateral to the spinous process. This approach visualizes the transverse process. The needle is inserted cranial-to-caudal to make contact with the shadow of the transverse process, with the needle tip deep to the fascial plane of the erector spinae muscle. Injection of saline confirms the location of the needle, and the anesthetic is injected.

All patients will receive PO acetaminophen and PO gabapentin the morning of surgery. Pt. will be placed on PRN oxycodone/acetaminophen (Percocet) postoperatively. PRN IV dilaudid may be given for severe breakthrough pain.

Opioid usage at 1, 24 and 48 hours after the block will be recorded by a member of the research team. Pain scores at rest and on movement will be measured by the investigator using Visual Analog Scale (VAS). Nausea will be measured using a categorical scoring system (none=0; mild=1; moderate=2; severe=3). Sedation scores will also be assessed by a member of the study team using a sedation scale (awake and alert=0; quietly awake=1; asleep but easily roused=2; deep sleep=3). All these parameters will be measured at 1, 24 and 48 hours after the blocks and patients will be encouraged to ambulate on postoperative day 1 under supervision. Their ambulation activity will be recorded.

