8.0 Statistical consideration

Primary outcome: VAS score at 24 and 48 hours

Primary Research Hypothesis: ESP block will provide lower postoperative pain scores compared to TAP block for laparoscopic hysterectomy as measured by VAS scores at 24 and 48 hours

Secondary outcomes: Narcotic usage after 1, 24 and 48 hours. Pain scores using VAS at rest and walking at 1, 24 and 48 hours. Nausea scores at 1, 24 and 48 hours. Sedation scores at 1, 24 and 48 hours. If the patient is discharged within 48 hours, every effort will be made to obtain data points. We will also assess patient satisfaction postoperative at 24 and 48 hours. We will also measure time to first flatus, incidence of urinary retention, incidence of respiratory depression, ambulation activity and hospital length of stay.

Secondary Research Hypotheses: ESP block will show improved patient satisfaction scores and decreased nausea and sedation scores compared to TAP block.

Statistical analysis will be performed using a standard statistical program (SAS or SPSS). All data will be summarized (means, standard deviations, standard errors, and ranges for continuous variables; frequencies and percentages for categorical variables) by group. Demographic data will be compared between the four groups using ANOVA or chi-square tests as appropriate. The primary outcome, VAS at 24 and 48 hours, will be compared between the groups using repeated measures ANOVA; the model will include fixed effects for group, time, and the group by time interaction and random effects to allow correlations between the two times and different variances for the two times. Pain and satisfaction scores and opioid usage over time will be analyzed using repeated measures ANOVA. Nausea and sedation scores will be compared between groups at each time point using Mantel-Haenszel chi-square tests for ordered categorical data. Time to first flatus will be compared using log-rank survival analysis; incidence of urinary retention, incidence of respiratory depression, and ambulation activity will be compared using chi-square tests; and hospital length of stay will be compared using Wilcoxon Rank Sum tests. Distributions of the continuous variables will be examined, and a transformation of the data (e.g. natural logarithm) or nonparametric tests will be used as necessary. A 5% significance level will

be used for all comparisons.

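### Patient blinding is claimed but not secured: ESP is placed preoperatively in the back, TAP after induction in the abdomen, and no masking step is described for a patient-rated primary outcome

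*Combined protocol and SAP*

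**What the plan says.** **Blinding.** Section 4.0: "Both the patients and the research staff doing assessments will be blinded to the randomization".

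**Timing.** Section 5.0: "The TAP blocks will be placed intraoperatively after induction, while ESP blocks will be done preoperatively".

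**Site.** For ESP, Section 4.0 specifies, on each side, "20ml injected at T8 and 20ml injected at T12", and Section 5.0 says that "the ultrasound is positioned in a parasagittal fashion, 2-3 inches lateral to the spinous process". For TAP, Section 5.0 says that "the ultrasound probe is placed transverse to the abdominal wall, between the iliac crest and the costal margin".

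**What patients are told.** Section 4.0 covers the contact before surgery: "They will be informed about the study and all questions will be answered". It does not say whether block timing or site is explained.

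**Preoperative drugs.** Section 5.0: "All patients will receive PO acetaminophen and PO gabapentin the morning of surgery". No sedative is named. Section 4.0 also refers to a standardized enhanced recovery pathway, whose contents are not given.

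**Outcome and hypothesis.** Section 8.0 makes VAS at 24 and 48 hours primary, with the hypothesis that "ESP block will provide lower postoperative pain scores compared to TAP block for laparoscopic hysterectomy". The hypothesis does not mention timing.

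**The concern.** The two arms differ in what a patient can experience. An ESP patient may be awake for injections on both sides of her back. A TAP patient is anaesthetised for hers, which are in the abdomen. If patients connect that experience with an arm, expectation could move the pain score in either direction. Section 5.0 has the investigator collect the VAS, but the rating is still the patient's, so a blinded assessor does not remove this route. Patient satisfaction, a secondary outcome with a directional hypothesis, is exposed in the same way.

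What is at stake is mainly the credibility of the claim. A report that repeats the Section 4.0 sentence would assert a protection that the written procedures do not provide. In addition, every ESP block is preoperative and every TAP block follows induction, so a difference between arms belongs to the block together with its timing.

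**Working it through.** **Step 1. Set the text side by side.**

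| Feature | ESP | TAP |
|---|---|---|
| When placed | Preoperatively | After induction |
| Where | Back, T8 and T12, both sides | Abdominal wall, both sides |
| Patient's state at placement | Not stated | Anaesthetised |
| Drug and volume | 266 mg Exparel (20 ml) plus 60 ml of 0.125% bupivacaine | Same |
| Masking step described | None | None |

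The drug and volume match, but timing and site do not. To identify her arm, an ESP patient would have to recall the injections and know what they signify. A TAP patient feels nothing at placement and could only infer her arm from what she was told.

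**Step 2. Reproduce the plan's figure.** Section 8.0 gives a coefficient of variation of 0.70, 40 per group, a ratio of means of 1.6, two-sided 5% tests and 90% power.

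- Log-scale SD: s = sqrt(ln(1 + 0.70²)) = sqrt(ln 1.49) = 0.6315.
- Effect: ln(1.6) = 0.4700.
- Standard error: 0.6315 × sqrt(2/40) = 0.1412.
- Noncentrality: 0.4700 / 0.1412 = 3.33. With 78 degrees of freedom, power is 90.8%.

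The stated 90% reproduces. Nothing in this point disputes it.

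**Step 3. Illustrate what awareness could do.** The documents give none of the following, so all are assumptions:

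- no true difference between blocks;
- a 10% lower VAS in each ESP patient who is aware of her arm;
- a share f of ESP patients aware;
- a correlation rho between the 24- and 48-hour scores of 0.5 to 1.0.

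The test is the group main effect, that is, the mean of the two times.

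- SD of the two-time mean: s × sqrt((1 + rho)/2) = 0.547, 0.599 and 0.6315 for rho = 0.5, 0.8 and 1.0.
- Shift: -ln(0.90) × f = 0.1054 × f.
- Example with rho = 0.5 and f = 1: standard error 0.547 × sqrt(2/40) = 0.122; noncentrality 0.1054 / 0.122 = 0.86; rejection probability 13.6%.

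False-positive probability on the log scale (nominal 5%):

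| rho | All ESP aware | Half aware | One quarter aware |
|---|---|---|---|
| 0.5 | 13.6% | 7.1% | 5.5% |
| 0.8 | 12.2% | 6.8% | 5.4% |
| 1.0 | 11.4% | 6.6% | 5.4% |

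On the raw scale (SD proportional to the mean, normal approximation) the same assumptions give about 10-12%, 6-7% and 5.3-5.4%.

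A shift in the opposite direction would favour TAP instead. It would work against a false finding of ESP benefit.

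**The case against.** The strongest reply is that the decisive facts lie outside the available text. Blinding fails only if patients can link what happened to them with an arm, and that depends on consent wording and on sedation for the ESP block. The consent pages were not available to this review, and the pathway's contents are not given. Acetaminophen and gabapentin are named, but the protocol does not say that they are the only preoperative drugs. A patient may receive a back injection and still not know which arm it represents. This stands, and it rules out a stronger reading: a reader might infer that patients are in fact unblinded, and the documents do not show that.

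The figures above also rest wholly on assumed values. A reader might take 10-14% as the trial's error rate. It is not: that range needs every ESP patient to be aware and all to shift by 10% in the same direction. Nothing in the plan says that patients expect ESP to be better. Section 1.0 describes TAP as the site's standard, and both arms receive an active block.

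Finally, a reader might call the overlap of block and timing an analysis error. It is not one. Section 5.0 states the timing openly, each block is compared as delivered, and no two-arm model could separate the two. It affects only how the conclusion is worded.

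What the reply does not remove is the gap itself. Section 4.0 asserts patient blinding, and the procedures, followed as written, do not provide it.

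**Conclusion.** The point holds in a limited form. Patient blinding is claimed but not secured for a patient-rated primary outcome. This rests on the text alone: different timing, different body site and no masking step in Sections 4.0 and 5.0. It goes beyond missing detail, because the plan asserts a property that its own procedures do not deliver.

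The size and direction of any bias are unknown. Under the assumed 10% shift, the effect ranges from near nominal (5.3-5.5%, a quarter of ESP patients aware) to a false-positive risk of roughly 10-14% (all aware). The sample size and power statement are unaffected. The point deserves correction because the remedy is cheap and the patients' guesses cannot be recovered reliably after the trial.

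**What to change.** 1. **If the site uses a masking step for ESP patients**, for example amnestic sedation with neutral patient information and dressings at both sites, write it into Section 5.0 and apply it to all patients. The Section 4.0 claim can then stay.
2. **If it does not**, replace the Section 4.0 sentence with wording such as: *Research staff who assess outcomes are blinded to allocation; patients are not assumed to be blinded.* Report the trial as assessor-blinded and state possible expectation bias as a limitation.
3. **In either case, word the conclusion** as ESP placed preoperatively versus TAP placed after induction.
4. **In either case, ask each patient once** which block she thinks she had, after the 48-hour VAS is recorded and out of the assessor's sight. A question at 1 or 24 hours would precede one or both primary ratings and could prime them.

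**Cost.** Amendment wording and one extra question per patient. No extra patients are needed, and block delivery need not change. The downsides are a weaker blinding claim under option 2, and a guess at 48 hours that partly reflects how well pain was relieved.

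### Outcome times are counted from the block, which is preoperative for ESP and intraoperative for TAP, so time zero differs by arm; the 1-hour readings and the opioid windows are affected most

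*Combined protocol and SAP*

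**What the plan says.** Section 5.0 (Study procedures) gives the only explicit anchor, and gives it twice. For opioids: "Opioid usage at 1, 24 and 48 hours after the block will be recorded by a member of the research team". For opioids, VAS, nausea and sedation together: "All these parameters will be measured at 1, 24 and 48 hours after the blocks". The same section sets the block timing by arm: "The TAP blocks will be placed intraoperatively after induction, while ESP blocks will be done preoperatively".

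Sections 2.0 and 8.0 repeat the hours without naming the event they count from. Section 2.0 has "The IV and PO opioid doses will be quantified at 1, 24, and 48 hours" and "We will also measure postoperative nausea and sedation scores at 1, 24 and 48 hours", and lists better postoperative pain scores among its aims. Section 8.0 has "Primary outcome: VAS score at 24 and 48 hours", and its primary hypothesis describes the pain scores as postoperative. Neither section applies that word to opioid use.

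In the analysis (section 8.0), the primary VAS model covers 24 and 48 hours only, with "random effects to allow correlations between the two times and different variances for the two times". The 1-hour data enter elsewhere: "Nausea and sedation scores will be compared between groups at each time point using Mantel-Haenszel chi-square tests", and pain and opioid use over time go into repeated measures ANOVA.

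**The concern.** Read together, the two rules in section 5.0 make the clock start at a different stage of the operation in each arm. A reading with the same nominal hour is then taken at a different time after surgery in ESP and in TAP.

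Two things are at stake. The first is the 1-hour reading, one of three time points for the secondary outcomes. An hour after a preoperative block the patient is very probably still under anaesthesia. She cannot give a VAS or nausea rating, a sedation score would describe the anaesthetic, and the opioid count would contain no postoperative time. The second is the opioid comparison, which is specific aim 1: a window of fixed length from an earlier block holds less postoperative time. The oral PRN opioid starts only after surgery, so that is the time that matters for it.

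**Working it through.** **The plan's own figure.** Section 8.0 gives 90% power from a coefficient of variation of 0.70, 40 per group, a ratio of means of 1.6 and a two-sided 5% test. Log-scale SD = sqrt(ln(1 + 0.70²)) = 0.631; ln(1.6) = 0.470. Power is 91.4% by the normal approximation and 90.8% by the noncentral t with 78 df. The figure is reproduced, and no block or reading time enters it.

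**Inputs for the timing check.** The documents give no durations, so these are assumptions:
- p, ESP block to induction: 0.25 to 1 h
- induction to incision: 0.25 h
- s, length of surgery: 1 to 3 h

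Opioid totals are taken as cumulative from the block, which the plan does not state.

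**Formulas.** Let b be the time from block to end of surgery. For ESP, b_E = p + 0.25 + s = 1.5 to 4.25 h. Postoperative time in a window of W hours is max(0, W − b). For W = 24 or 48, the ESP shortfall relative to TAP is (b_E − b_T)/(W − b_T).

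| TAP placed | b_T | Gap between arms | 24 h shortfall | 48 h shortfall |
|---|---|---|---|---|
| Directly after induction | s + 0.25 = 1.25 to 3.25 h | 0.25 to 1 h | 0.25/22.75 = 1.1% to 1/20.75 = 4.8% | 0.25/46.75 = 0.5% to 1/44.75 = 2.2% |
| At incision | s = 1 to 3 h | 0.5 to 1.25 h | 0.5/23 = 2.2% to 1.25/21 = 6.0% | 0.5/47 = 1.1% to 1.25/45 = 2.8% |
| At end of surgery | 0 h | 1.5 to 4.25 h | 1.5/24 = 6.3% to 4.25/24 = 17.7% | 1.5/48 = 3.1% to 4.25/48 = 8.9% |

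The first row is the plainest reading of section 5.0. The last is permitted by its wording but not stated.

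**1-hour window (W = 1).** ESP has 0 h of postoperative time, because b_E is at least 1.5 h. TAP has 0 h in the first two rows and 1 h in the last. So either neither arm has a usable 1-hour score, or only TAP does.

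**If opioids are recorded by interval instead.** The 24 to 48 h interval is wholly postoperative in both arms, so its shortfall is 0%. The 1 to 24 h shortfall equals the 24 h column in the first two rows. In the last row it is 0.5/23 = 2.2% to 3.25/23 = 14.1%.

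**A second set of assumptions.** Let ESP precede TAP by 0.5 to 3 h, with TAP placed 0 to 2 h before the end of surgery. The shortfall is then 0.5/24 = 2.1% to 3/22 = 13.6% at 24 h, and 0.5/48 = 1.0% to 3/46 = 6.5% at 48 h. Its extreme case, TAP at end of surgery with a gap of only 0.5 h, puts the 1-hour ESP reading 0.5 h after surgery. Induction and the whole operation would then have to fit into half an hour.

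**The case against.** The best defence is that a postoperative anchor was meant, since sections 2.0 and 8.0 describe the pain scores as postoperative and section 2.0 says the same of nausea and sedation. But neither section names an event, and section 5.0, which staff would follow, names the block twice. If end of surgery was intended, the text still needs correcting.

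Other objections limit the point, and they stand:
- A reader might infer that the sections contradict each other on opioids. They do not: no section calls opioid use postoperative. For opioids the problem is unequal postoperative time.
- A reader might infer that all 1-hour data are lost. Opioid use to 1 hour can still be recorded; only the patient-assessed scores become unobtainable or uninformative.
- A reader might infer that the opioid comparison is tilted towards ESP. Less postoperative time does lower the ESP count. However, any intraoperative opioid given between the two block times would count only in ESP. Section 5.0 names no such opioid, so that effect may be zero, but the net direction is not known. Nor is a percentage of postoperative time the same as a percentage of opioid use.
- The largest shortfalls need TAP at the end of surgery.
- Any anchor leaves one clock unequal: counting from the block equalises time since injection, counting from surgery equalises time since surgery.

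**Conclusion.** The point holds and should be fixed. That time zero differs by arm follows from the text of section 5.0 and needs no assumption. The 1-hour ESP reading falls before the end of surgery whenever ESP block to end of surgery exceeds 1 h. If TAP is placed late, the 1-hour readings exist in both arms only nominally and cannot be compared.

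The opioid shortfall in ESP is small on the plainest reading and reaches its upper range only with TAP at the end of surgery. All sizes rest on the assumed durations.

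A reader might infer that the primary result is compromised. The documents do not support that. The primary model excludes the 1-hour reading, and its 24- and 48-hour VAS readings are offset by the same gap between arms, probably with little effect. The 24- and 48-hour nausea and sedation tests do not use the 1-hour data either. The harm is confined to secondary outcomes: one of three time points, and the opioid comparison.

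**What to change.** Reconcile sections 2.0, 5.0 and 8.0 by naming one time zero common to both arms for VAS, opioid use, nausea and sedation, such as end of surgery or PACU arrival. Count postoperative opioids from that point and report intraoperative opioids separately. Record block time and end-of-surgery time for every patient. No change to the timing of either block is proposed.

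The downside is that readings would be at unequal time since injection, 0.25 to 4.25 h longer in ESP under the assumptions above. The background statement of analgesia for up to 72 hours is a maximum and does not show that the effect is constant, so this cannot be dismissed. A sensitivity analysis adjusting for time since block helps only where the arms overlap. At end of surgery, ESP would be at 1.5 to 4.25 h and TAP at 1.25 to 3.25 h if placed directly after induction, which overlap. If TAP is placed at the end of surgery it would be at 0 h, with no overlap, and adjustment could not separate time since block from arm. In that case, report time since block by arm instead.

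The cost is protocol and data-form wording, two recorded times per patient, separate capture of intraoperative opioids and, where informative, one sensitivity analysis. The number of patient assessments and the sample size stay the same.
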